## NON-INTERVENTIONAL (NI) STUDY PROTOCOL

## **Study Information**

Title	Tafamidis Pregnancy Surveillance Study	
Protocol number	B3461091	
Protocol version identifier	1.0	
Date	28 April 2020	
EU Post Authorization Study (PAS) register number	Study not yet registered	
Active substance	Tafamidis PF-06291826	
Medicinal product	Vyndaqel (tafamidis meglumine) 20 mg capsules	
	Vyndamax (tafamidis) 61 mg capsules	
Product reference	Not applicable	
Procedure number	Not applicable	
Marketing Authorization Holder(s) (MAH)	FoldRx, a wholly owned subsidiary of Pfizer, Inc. [name]	
Joint PASS	No	
Research question and objectives	This descriptive non-interventional study of women diagnosed with ATTR exposed to tafamidis during or within 1 month prior to pregnancy is intended to assess the risks to pregnancy outcomes and possible adverse effects on the developing fetus and neonate.	

	Objectives –
	1. Describe birth outcome frequency within the reported pregnancy outcomes (live full term or premature birth, spontaneous or induced abortion, and stillbirth) in women with ATTR exposed to tafamidis during or within 1 month prior to pregnancy.
	2. Describe the frequency of reported fetal neonate, and infant outcomes within the reported pregnancies (major congenital malformations/anomalies [overall and specific], low birth weight, small for gestational age (SGA), preterm birth, low Apgar score at 1 and 5 minutes, and infant milestone status at 6 and 12 months) following tafamidis exposure in women ATTR during and 1 month prior to pregnancy.
Countries of study	Global
Author	[name], MBA Global Product Development Pfizer Inc [name] [contact] Email: [contact]

This document contains confidential information belonging to Pfizer. Except as otherwise agreed to in writing, by accepting or reviewing this document, you agree to hold this information in confidence and not copy or disclose it to others (except where required by applicable law) or use it for unauthorized purposes. In the event of any actual or suspected breach of this obligation, Pfizer must be promptly notified.

## **1. LIST OF ABBREVIATIONS**

Abbreviation	Definition	
AE	Adverse event	
ATTR	Transthyretin amyloidosis	
ATTR-CM	Transthyretin amyloid cardiomyopathy	
ATTR-PN	Transthyretin amyloid polyneuropathy	
AUC	Area under the curve	
СМ	Cardiomyopathy	
CRF	Case report form	
СТ	Clinical trial	
DCT	Data collection tool	
DSU	Drug safety unit	
EDP	Exposure during pregnancy	
ENCePP	European network of centres for pharmacoepidemiology and pharmacovigilance	
EU	European Union	
FDA	Food and drug administration	
HED	Human equivalent dose	
НСР	Health care professional	
Leu111Met	Leucine replaced by methionine at position 111	
MedDRA	Medical dictionary for regulatory activities	
MRHD	Maximum recommended human dose	
NIS	Non-Interventional Study	
PAM	Post-authorization measure	
PASS	Post-authorization safety study	
PIL	Patient information leaflet	
PMR	Post-marketing requirement	
PN	Polyneuropathy	
PSUR	Periodic safety update report	
PV	Pharmacovigilance	
RMP	Risk Minimization Plan	
SAE	Serious adverse event	
SGA	Small for gestational age	
SmPC	Summary of product characteristics	
TESPO	Tafamidis Enhanced Surveillance for Pregnancy Outcomes	
THAOS	Transthyretin Amyloidosis Outcomes Survey	
TTR	Transthyretin	
TTR-FAP	Transthyretin familial amyloid polyneuropathy	
US	United States	

PFIZER CONFIDENTIAL

CT24-WI-GL02-RF02 1.0 Non-Interventional Study Protocol Template For Secondary Data Collection Study 15-Aug-2018 Page 5 of 42

USPI	US package insert
USPPI	US patient package insert
Val30Met	Valine replaced by methionine at position 30
Val122Ile	Valine replaced by isoleucine at position 122

## **Country Coordinating Investigators**

Not Applicable.

## **3. ABSTRACT**

Title: Tafamidis Pregnancy Surveillance Study

**Rationale and background:** VYNDAQEL® (tafamidis meglumine 20 mg capsule) once daily was first approved in the European Union (EU) for transthyretin amyloid polyneuropathy (ATTR-PN), also known as transtheyretin familial amyloid polyneuropathy (TTR-FAP) under exceptional circumstances on 16 November 2011. The product has been approved for ATTR-PN in over 40 other countries since then. The Tafamidis Enhanced Surveillance for Pregnancy Outcomes (TESPO), a worldwide approach to enhanced surveillance of pregnancy and birth outcomes in women with ATTR-PN exposed to tafamidis, was implemented as an additional pharmacovigilance activity in the EU Risk Minimization Plan (RMP), classified as a category 3 post-authorization measure (PAM), and has been in effect since 2011.

The original TESPO program was amended to broaden the scope from women with ATTR-PN to also include women with transthyretin amyloid cardiomyopathy (ATTR-CM), exposed to tafamidis and to also include all formulations and dosage forms (20 mg tafamidis meglumine and 61 mg tafamidis free acid).

On 03 May 2019, with the US approval of VYNDAQEL® once daily at a dose of 80 mg (tafamidis meglumine 4 x 20 mg capsules), and VYNDAMAX® (tafamidis 61 mg capsule) once daily for transthyretin amyloidcardiomyopathy (ATTR-CM), Food and Drug Administration (FDA) required a worldwide pregnancy surveillance study in women with ATTR exposed to tafamidis meglumine and tafamidis (henceforth collectively referred to as "tafamidis") during pregnancy to assess the risks of pregnancy complications and adverse effects on the developing fetus and neonate. To meet this post-marketing requirement (PMR 3576-1), this study will describe birth outcome frequency within the reported pregnancies in women with ATTR exposed to tafamidis during or within 1 month prior to pregnancy included in the ongoing TESPO surveillance program and/or standard exposure during pregnancy (EDP) and follow-up information collected in interventional studies.

**Research Question and Objectives:** This global, prospective, non-interventional study of women with ATTR exposed to tafamidis during or within 1 month prior to pregnancy is intended to assess the risks to pregnancy outcomes and possible adverse effects on the developing fetus and neonate.

The specific objectives are:

1. Describe birth outcome frequency within the reported pregnancies (live full term or premature birth, spontaneous or induced abortion, and stillbirth) in women with ATTR exposed to tafamidis during or within 1 month prior to pregnancy.

2. Describe the frequency of reported fetal, neonate and infant outcomes within the reported pregnancies (major congenital malformations/anomalies [overall and specific], low birth weight, small for gestational age (SGA), preterm birth, low Apgar score at 1 and 5 minutes, and infant milestone status at 6 and 12 months) following tafamidis exposure in women with ATTR during or within 1 month prior to pregnancy.

**Population:** Women diagnosed with ATTR who received tafamidis during pregnancy or who became pregnant within 1 month after discontinuation of tafamidis reported as EDP events in interventional or non-interventional clinical studies in the tafamidis development program, via spontaneous reports, solicited cases or compassionate use reports, and who agreed to release information from their obstetric and pediatric healthcare provider will be included in this study.

**Study Design**: This is a global, prospective, non-interventional study designed to collect and report information obtained via TESPO and/or standard EDP and follow-up information on outcomes of events of pregnancy in women with ATTR exposed to tafamidis during pregnancy or who became pregnant within 1 month after discontinuation of drug.

**Variables:** Variables to be evaluated in this study include patient medical /obstetrical history, pregnancy status and outcomes, and neonate and infant development status at birth, 6 and 12 months of age.

**Data Sources:** Events of pregnancy reported in female patients with ATTR receiving tafamidis via clinical trials, non-interventional trials, through direct contact from patients and health care professionals using the toll-free numbers provided in the labeling documents, through unsolicited requests for pregnancy safety information (via Pfizer Medical Information Department) or through contact with sales representatives. Information regarding how to contact the Sponsor (per country specific labeling guidelines) in the event of a pregnancy exposure is provided in the summary of product characteristics (SmPC), the US package insert (USPI), the patient information leaflet (PIL), and in informational materials provided (e.g., scientific meetings and direct communication) to health care professionals (HCPs).

**Study Size:** Sample size calculation is not applicable. In this descriptive study all female patients diagnosed with ATTR reported as having tafamidis exposure during or within 1 month of pregnancy will be included.

**Data Analysis:** Given the expected low number of pregnancy exposures, no formal data analysis or hypothesis testing will be conducted. Data collected on exposure and outcomes will be summarized descriptively. Women with ATTR exposed during pregnancy to concomitant medications with a known increased risk for congenital anomalies will be excluded from the descriptive summary but will be included in the study and described separately. A separate descriptive summary based on prospective and retrospective cases will be performed and submitted to the FDA. Prospective cases are defined as women who

#### PFIZER CONFIDENTIAL

CT24-WI-GL02-RF02 1.0 Non-Interventional Study Protocol Template For Secondary Data Collection Study 15-Aug-2018 Page 9 of 42 enroll prior to the occurrence of the pregnancy outcome (live birth, miscarriage, stillbirth, pregnancy termination). Retrospective cases are defined as women who enroll or contact the registry after the pregnancy outcome has occurred (live birth, miscarriage, stillbirth, pregnancy termination). Stratified analysis of the reported pregnancy outcomes, including pregnancies in women reported prior to start of this protocol, will be performed by daily maternal dose.

**Milestones:** With the protocol finalized in April 2020, the trial will initiate shortly thereafter and data collection will end in June 2030. Annual interim reports and the final study report will be submitted to the FDA according to committed timelines (Interim: April 2021, April 2022, April 2023, April 2024, April 2025, April 2026, April 2027, April 2028, April 2029, April 2030; Final Report: December 2030).

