## 6. RATIONALE AND BACKGROUND

VYNDAQEL® (tafamidis meglumine 20 mg capsule) once daily was first approved in the EU for transthyretin amyloid polyneuropathy (ATTR-PN), also known as transthyretin familial amyloid polyneuropathy (TTR-FAP) under exceptional circumstances on 16 November 2011. The product has been approved for ATTR-PN in over 40 other countries since then. TESPO, a worldwide approach to enhanced surveillance of pregnancy and birth outcomes in women with ATTR-PN exposed to tafamidis, was implemented as an additional pharmacovigilance activity in the EU Risk Minimization Plan (RMP), classified as a category 3 post-authorization measure (PAM), and has been in effect since 2011. As of 25 September 2019, there were 20 cases of exposure in utero to tafamidis, of which 13 were maternal exposure, during or within 1 month prior to pregnancy in the overall tafamidis program (clinical and non-interventional studies: Fx-005 (1); Fx1A-303 (2); Transthyretin Amyloidosis Outcomes Survey [THAOS](17).

On 03 May 2019, with the US approval of VYNDAQEL® once daily at a dose of 80 mg (tafamidis meglumine 4 x 20 mg capsules), and VYNDAMAX® (tafamidis 61 mg capsule) once daily for transthyretin amyloid cardiomyopathy (ATTR-CM), FDA required a post-marketing requirement (PMR 3576-1). To meet this post-marketing requirement (PMR 3576-1), this study will describe birth outcome frequency within the reported pregnancies in women with ATTR exposed to tafamidis during or within 1 month prior to pregnancy that are collected using the ongoing TESPO surveillance program and/or standard EDP and follow-up information collected in interventional studies.

In addition to US approval, tafamidis for the treatment of patients with ATTR-CM has been approved in Japan, United Arab Emirates, Brazil Canada, European Union, Singapore, Switzerland and Australia at this time.

This descriptive non-interventional study is designated as a Post-Authorization Safety Study (PASS) and is a commitment to the US FDA.

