## 6.2.2. Relevant Nonclinical Findings

There was no evidence of adverse effects of tafamidis on fertility, or reproductive performance, or mating behavior in rats. In animal reproductive studies, oral administration of tafamidis meglumine to pregnant rabbits during organogenesis resulted in adverse effects on development (embryofetal mortality, fetal body weight reduction and fetal malformation) at a dose providing approximately 9 times the human exposure area under the curve (AUC) at the maximum recommended human dose (MRHD), and increased incidence of fetal skeletal variations at a dose providing equivalent human exposure (AUC) at the MRHD. Postnatal mortality, delayed male sexual maturation, and impaired learning and memory were observed in offspring of pregnant rats administered tafamidis meglumine during gestation and lactation at a dose approximately 2 times the MRHD based on body surface area (mg/m^2).

Nonclinical studies with tafamidis indicate that there are no effects on the male germ cell before conception. In toxicology studies there was no evidence of genotoxicity, no histopathological changes in testis or epididymis and no effects on male fertility at doses up to 30 mg/kg. Therefore, the risk for male-mediated developmental toxicity is considered to be low because the levels of tafamidis estimated to be transferred in semen are significantly lower than the concentrations that cause developmental toxicity in nonclinical studies.

In summary, anomalies have been observed in rabbit and rat reproductive toxicology studies. In humans, ATTR could present during the patient's reproductive years, although based on our current understanding of age of onset of disease, this is more likely for a patient with ATTR-PN rather than ATTR-CM. On account of the low prevalence of ATTR-PN and ATTR-CM (rare diseases), limited reproductive data are available in humans. There has been a low incidence of exposures reported in women with ATTR-PN in the ongoing TESPO surveillance program from clinical and NI studies over a 7-year period. Nonetheless, given that tafamidis meglumine/tafamidis may cause fetal harm, product labeling recommends avoidance of pregnancy in female patients receiving tafamidis; breastfeeding is also not recommended during treatment with tafamidis. B3461091 will collect and summarize data on pregnancy outcome and birth outcome in women with ATTR exposed to tafamidis during or within 1 month prior to pregnancy.

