## 8. RESEARCH METHODS

## 8.1. Study Design

This is a global, prospective, non-interventional study designed to collect information on pregnancy outcomes in women with ATTR exposed to tafamidis during or who became pregnant within 1 month after discontinuation of drug.

[figure not shown]
This PMR study (B3461091), which is anticipated to start in 2020 and complete in 2030 will utilize routine pharmacovigilance activities in addition to the data collection and process implemented via the ongoing Tafamdis Enhanced Surveillance for Pregnancy Outcomes (TESPO) program, which will be maintained at least until 2030. Time of enrollment is the time of initial awareness of the pregnancy reported by an investigator (clinical trial) or the HCP or patient (non-clinical source). Once initiated, all prospective pregnancy events captured via Study B3461091 (including new data collected in TESPO) will be reported to regulatory agencies in aggregate reports via Study B3461091.

TESPO is descriptive, non-interventional, observational program which has been ongoing since 2011 as an EMA post marketing requirement to assess outcome of pregnancy and birth outcomes (including major birth defects and/or developmental abnormalities in live born children up to 12 months) in female patients with ATTR-PN with exposure to tafamidis during or within 1 month prior to the pregnancy. All TESPO data are collected through use of the standard pharmacovigilance EDP form and follow-up form and the Tafamidis Enhanced Surveillance data capture aid (DCA) and 12-month follow up forms. Collection of data will be updated to include ATTR-CM. Updates will also include maternal assessment at mid-point during pregnancy and 6 month assessment of infant in addition to timepoints already collected. This collection will be achieved by adding a non-standard data collection time point (triggered at 2nd trimester of gestation) and at 6 months post delivery using the standard EDP Follow-Up Form. The data are stored in the Pfizer safety database (ARGUS) and reported with routine pharmacovigilance activities. Below is a schematic of the TESPO study design (Figure 1).

Figure 1. Study Population Flow Diagram

- Women exposed to tafamidis meghumine/tafamidis during pregnancy or who became pregnant within 1 month after discontinuation of drug
- During the data collection period of April 2020 June 2030
- No exclusions

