## 8.2.1. Inclusion Criteria

Patients must meet all of the following inclusion criteria to be eligible for inclusion in the study:

All women diagnosed with ATTR exposed to tafamidis during or within 1 month prior to pregnancy, reported as exposure during pregnancy (EDP) events in interventional or non-interventional clinical studies in the tafamidis development program, via spontaneous reports, solicited cases or compassionate use reports, will be included in study B3461091.

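### The protocol does not settle whether pregnancies reported before April 2020 count in the Objective 1 and 2 frequencies: Figure 1, section 8.2.1 and section 8.7 disagree

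*Protocol*

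**What the plan says.** Three parts of the protocol bear on which pregnancies are counted.

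- **Section 8.1, Figure 1.** The list with the population diagram carries the line "During the data collection period of April 2020 June 2030". The text of 8.1 adds that, once the study is initiated, "all prospective pregnancy events captured via Study B3461091 (including new data collected in TESPO) will be reported to regulatory agencies in aggregate reports". Section 8.1 also defines enrolment as the time of first awareness of the pregnancy.
- **Sections 8.2.1, 8.2.2 and 7.** The inclusion criterion takes all women with ATTR and the relevant exposure, "reported as exposure during pregnancy (EDP) events in interventional or non-interventional clinical studies in the tafamidis development program" or through spontaneous, solicited or compassionate-use reports. There are no exclusion criteria. The objectives refer to the reported pregnancies. None of these sets a date limit.
- **Abstract (Data Analysis) and section 8.7.** Earlier pregnancies are named in one place: the stratified analysis of reported pregnancy outcomes, "including pregnancies in women reported prior to start of this protocol, will be performed by daily maternal dose".

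Section 6 shows that such cases exist. As of 25 September 2019, "there were 20 cases of exposure in utero to tafamidis, of which 13 were maternal exposure".

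**The concern.** Two analysts could build different denominators for malformation, preterm birth or low birth weight, and each could cite the protocol. One would follow Figure 1 and count only April 2020 onwards. The other would follow 8.2.1 and count every reported case.

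The narrower reading is a natural one. If earlier cases were already in the population, there would be little reason to add them expressly to one analysis, and the word "new" in the 8.1 sentence on TESPO data points the same way. On that reading the dose table holds pregnancies that the overall table lacks, so the strata cannot sum to the total.

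Section 8.9 names the small number of pregnancies as the first limitation, so losing cases from the main frequencies is costly. Section 8.1 says that TESPO data are collected on the exposure-during-pregnancy form, its follow-up form, the TESPO data capture aid and the 12-month form. The additions are ATTR-CM, a mid-pregnancy assessment and a 6-month infant assessment. Most Objective 2 items therefore already have a collection route for earlier cases.

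**Working it through.** **Inputs from the protocol**

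- Cases held at 25 September 2019: 20, of which 13 maternal (section 6).
- Source split: "Fx-005 (1); Fx1A-303 (2); Transthyretin Amyloidosis Outcomes Survey [THAOS](17").
- First approval: "under exceptional circumstances on 16 November 2011" (section 6). TESPO has been in effect since 2011.
- Alternative accrual period: exposures "in the ongoing TESPO surveillance program from clinical and NI studies over a 7-year period" (section 6.2.2).
- Study window: 28 April 2020 (protocol date) to 30 June 2030, which is 10.17 years.

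**The protocol's own count.** 1 + 2 + 17 = 20, as stated. The 13 maternal cases cannot be re-derived, because no maternal split by source is given.

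**Assumption.** The protocol gives no expected number and no future rate. The share below takes a constant rate r = 13 / T, where T is the past accrual period, itself assumed because section 6 does not say when counting began.

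**Share of earlier cases** = 13 / (13 + r × 10.17). The gap from 25 September 2019 to 28 April 2020 is 0.59 years. The last column adds r × 0.59 cases to the earlier group.

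| Past period T | r per year | New cases in window | Earlier share, 13 only | Earlier share with gap |
|---|---|---|---|---|
| 7 years | 1.86 | 18.9 | 40.8% | 42.7% |
| 16 Nov 2011 to 25 Sep 2019, 7.86 years | 1.65 | 16.8 | 43.6% | 45.4% |
| 1 Jan 2011 to 25 Sep 2019, 8.73 years | 1.49 | 15.1 | 46.2% | 47.8% |

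The middle row in full: 13 / 7.86 = 1.65 per year; 1.65 × 10.17 = 16.8; 13 / 29.8 = 43.6%. With 1.0 gap case, 14.0 / 30.8 = 45.4%. Shares are computed from unrounded values.

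**If the future rate differs from 1.65 per year**

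| Multiple of past rate | New cases | Earlier share, 13 only |
|---|---|---|
| 0.5 | 8.4 | 61% |
| 1 | 16.8 | 44% |
| 1.5 | 25.2 | 34% |
| 2 | 33.7 | 28% |
| 3 | 50.5 | 20% |

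The past count is itself imprecise: the exact 95% Poisson interval for 13 is 6.9 to 22.2, or 0.53 to 1.71 times the observed count.

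**Precision with zero events.** The exact two-sided 95% upper limit is 1 − 0.025^(1/n), assuming one assessable infant per pregnancy.

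- n = 17 (post-start only): 19.5%.
- n = 30 (13 + 16.8, rounded): 11.6%.
- n = 31 (with the gap case): 11.2%.

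**The case against.** **No sentence excludes the earlier cases.** A reader might infer that they enter the dose table and nothing else. The protocol does not say so. The 8.7 sentence on overall summaries covers events reported via TESPO or entered in the safety database, without a date limit, and the data source, study size and objectives carry none either. This stands: the defect is a contradiction, not a settled exclusion.

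**Late reports are not clearly lost.** A reader might infer that a pregnancy exposed before April 2020 and first reported later belongs to neither group. That requires Figure 1 to date the exposure. Its date line is separate from the exposure line, and 8.1 enrols by first awareness, so such a pregnancy can be enrolled within the window. If its outcome has already occurred, it meets the definition of a retrospective case. This stands.

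**The dose analysis may already show infant outcomes.** Section 8.6.1 uses pregnancy outcomes broadly enough to cover birth defects and developmental deficits. Earlier malformations could therefore appear in the dose table even on the narrow reading. This softens the loss but leaves the overall frequencies without those cases.

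**Post-start cases alone could be a defensible choice.** The study is described as prospective, and two scheduled assessments are new. That is fair, but the protocol would have to state the choice, and 8.2.1 reads otherwise. Table layout can be left to the analysis plan; who belongs to the study population cannot.

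**The share is not a protocol figure.** This stands. The scope widens to ATTR-CM, in which section 6.1 expects very few pregnancies, and section 8.9 promises efforts to raise awareness, so a constant rate may not hold. The share can only be given as an assumption with its range.

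**Conclusion.** The contradiction is real and should be resolved in the protocol. Figure 1 restricts the population by date, 8.2.1, 8.2.2 and the objectives do not, and earlier pregnancies are named only in the stratification by daily maternal dose. Following Figure 1 removes at least 13 known maternal exposures from the Objective 1 and 2 frequencies and puts the overall and dose-stratified results on different populations.

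The 13 is the protocol's figure. The share it represents by June 2030 is conditional: about 41-48% at a constant rate, depending on the accrual period and the gap, and about 20-61% for a future rate of 3 to 0.5 times the past one. The gain in precision, from 19.5% to about 11-12% for zero events, also depends on the constant rate and on one assessable infant per pregnancy. The documents do not support saying that earlier cases are definitely excluded, or that early exposures reported late fall out of the study.

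**What to change.** 1. State one population rule in Figure 1, 8.2.1 and 8.7: all maternal-exposure pregnancies, assigned by date of first report to the sponsor, up to the data cut-off. This agrees with the awareness-based enrolment definition in 8.1.
2. Summarise Objectives 1 and 2 for cases first reported before study start, cases first reported from study start, and the total, keeping the prospective and retrospective split.
3. Base the dose table on the same set, so that its strata can be reconciled with the total.
4. Show items collected only since the update (mid-pregnancy and 6-month assessments) for post-start cases only.

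The cost is protocol wording and a wider summary from the safety database. Section 8.7 already needs the earlier cases for the dose analysis. The small downside is that earlier cases had fewer scheduled contacts, which the separate columns make visible.
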